#### **5.4 Replacement of Subjects**

Subjects may not be replaced from this study.

#### **5.5 Study Termination**

This trial can be terminated by the sponsor at any time for any reason.

## 6 INVESTIGATIONAL PRODUCT

### 6.1 Formulation

Roxadustat is supplied by FibroGen, Inc. as red coated, oval tablets for oral administration, in strengths of 20 mg, 50 mg, and 100 mg. The excipients include lactose monohydrate, microcrystalline cellulose, povidone, croscarmellose sodium, magnesium stearate, and colorant Red Opadry II. All ingredients used for manufacture of roxadustat comply with US and European Union compendia or regulatory standards. Strengths are different in size and debossing reflects the strength (ie, 20, 50, or 100 mg). Due to the light-sensitive nature of roxadustat and to minimize exposure of the active pharmaceutical ingredient to light, tablets should remain in the original packaging for as long as possible and be administered as intact tablets only.

### 6.2 Storage

Roxadustat tablets should be protected from light, and stored at room temperature between 15°C and 30°C (59°F to 86°F).

Epoetin alfa should be stored according to the package insert.

All study drugs (roxadustat and epoetin alfa) should be stored in a securely locked area to which access is limited to appropriately authorized study personnel.

### 6.3 Study Drug Handling and Disposal

All study drugs provided by the Sponsor or provided at the study site should be retained at the site until otherwise instructed in writing by the Sponsor. Upon completion of the study or termination of the investigational site, all used (vials/syringes or bottles), unused, and partially used study drugs; and all study drugs that were not dispensed will be shipped to a site designated by the Sponsor or may be destroyed according to local/institutional policies by the Pharmacy/authorized staff after drug accountability and reconciliation has been completed by Sponsor. Please refer to the Study Reference Manual or Pharmacy Manual for additional information.

### 6.4 Route of Administration and Dose

#### 6.4.1 Roxadustat

Subjects on HD or PD or HHD randomized to roxadustat will take doses TIW for the entire duration of the Treatment Period. If a subject requires < 20 mg TIW (ie, < 60 mg per week) to maintain a Hb level of approximately 11 g/dL, the dosing frequency should be reduced in a step-wise fashion e.g. TIW to BIW, BIW to QW, QW to Q-2 Week etc.

Roxadustat will be dispensed to subjects with instructions for self-administration of the tablets orally on each dosing day, according to the dosing schedule. The tablets are to be swallowed whole.

First dose of roxadustat should be administered on Day 1 after completion of all procedures including laboratory draws. Roxadustat doses should be administered at least 2 days apart, and no more than 4 days apart. Dosing should occur at approximately at the same time of day. Roxadustat can be taken with or without food.

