### Notes:

#### *Dose Increases and Reductions:*

- Dose increases (↑) and reductions (↓) are preset.
- The dose steps are as follows: 20, 40, 50, 70, 100, 150, 200, 250, 300, and 400 mg. For example, a subject previously receiving 70 mg of roxadustat requiring a dose increase would have his dose changed to 100 mg of roxadustat. A subject previously receiving 150 mg of roxadustat requiring a dose reduction would have his dose changed to 100 mg of roxadustat. If < 20 mg /dose is required, dosing frequency should be reduced in a step-wise fashion e.g. TIW to BIW, BIW to QW, QW to Q-2 Week etc.
- The maximum dose is capped at 400 mg or 3.0 mg/kg/dose (whichever is lower).

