3 STUDY DESIGN

This Phase 3, multi-center, open-label, randomized, active-controlled study is designed to evaluate the efficacy and safety of roxadustat compared to epoetin alfa for the maintenance of hemoglobin levels in subjects on stable hemodialysis (HD) or peritoneal-dialysis (PD) and newly initiated dialysis (NID) originally on erythropoiesis-stimulating agent (ESA) for treatment of anemia.

A total of up to 1200 subjects are planned to be randomized to receive roxadustat or epoetin alfa (active control) in a 1:1 ratio, respectively.

For subjects randomized to roxadustat, the initial roxadustat dose will be determined using a conversion table based on the subject's previous average weekly prescribed ESA dose in the last 4 weeks prior to randomization if the subject is on epoetin or darbepoetin, and average monthly (4 weeks) prescribed ESA dose in 8 weeks prior to randomization if the subject is on Mircera[®] (Table 1).

If the mean qualifying screening hemoglobin value at randomization is less than the lower limit of the target hemoglobin range (i.e. <10 g/dL), the starting roxadustat dose will be increased by one dose step. If the converted initial dose exceeds the maximum dose of 3.0 mg/kg then the lower dose step should be chosen as the initial dose. Roxadustat will be dosed three times weekly (TIW) for the entire duration of the Treatment Period. Dosing frequency may only be adjusted to BIW or QW if a subject requires < 20 mg TIW (i.e., < 60 mg per week) to maintain an Hb level of approximately 11 g/dL.

Table 1. Initial Dosing of Roxadustat: Conversion Table from ESAs to Roxadustat

Epoetin (i.e., alfa, beta, theta, zeta, delta, or omega) ^a (IU/week)	Darbepoetin alfa^{a, b} (µg/week)	Mircera^{®c} (µg/ monthly)	Roxadustat Dose^d (mg/dose) TIW
< 5,000	< 25	< 80	70
5,000 to 8,000	25-40	80-120	100
> 8,000 to 16,000	> 40-80	> 120-200	150
> 16,000	> 80	> 200	200

a Average weekly prescribed dose in last 4 weeks prior to randomization

b If darbepoetin is used biweekly, use half the dose to get per week dose

c Average prescribed monthly (4-wks) dose in last 8 weeks prior to randomization

d Starting dose will be one step higher if the mean hemoglobin at randomization is < 10.0 g/dL, however, not to exceed 3.0 mg/kg/dose.

Notes: The roxadustat dose steps are 20, 40, 50, 70, 100, 150, 200, 250, 300, and 400 mg.

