Hemoglobin change from baseline to the average hemoglobin value of the Week 96 to 104 weeks of treatment will be analyzed using an MI ANCOVA model with baseline hemoglobin as a covariate, and treatment group and stratification factors except mean qualifying screening hemoglobin (≤ 10.5 vs. >10.5 g/dL) as fixed effects, using the Hb mean from the non-missing weeks.

In this study, there are patients in whom roxadustat dose frequency needed to be reduced to BIW or QW as part of their dose reduction below the lowest possible TIW dose of 20 mg TIW during treatment, to evaluate Hb maintenance, the following summary will be provided for these subgroups of subjects treated on BIW or QW (including any frequency $<QW$) for longer than 8 weeks (i.e., ≥ 56 days):

- Average Hb values over time for every 4-8 weeks after the initiation of BIW or QW
- Average weekly dose over time for every 4-8 weeks after the initiation of BIW or QW

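### Protocol 6.4.1 sets an unqualified 2-to-4-day dose spacing that the QW and every-2-weeks roxadustat schedules in the same section cannot meet, and the SAP is not consistent about which reduced frequencies exist

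*Protocol*

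**What the plan says.** Protocol Section 6.4.1 gives three instructions in sequence.

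1. Default: subjects randomized to roxadustat "will take doses TIW for the entire duration of the Treatment Period".
2. Exception: "If a subject requires < 20 mg TIW (ie, < 60 mg per week") to hold Hb near 11 g/dL, then "the dosing frequency should be reduced in a step-wise fashion e.g. TIW to BIW, BIW to QW, QW to Q-2 Week etc".
3. Spacing, two paragraphs later: "Roxadustat doses should be administered at least 2 days apart, and no more than 4 days apart".

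The step-down wording recurs in the Synopsis (Dose Adjustments), in Sections 2.6 and 4.5.3.1, and in Appendix 2, where the notes on dose increases and reductions again say that "dosing frequency should be reduced in a step-wise fashion e.g. TIW to BIW, BIW to QW, QW to Q-2 Week etc". The spacing sentence appears only in Section 6.4.1.

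The SAP says in its Section 1 that it elaborates Amendment 2 of the protocol. Its Section 3 states: "Dosing frequency may only be adjusted to BIW or QW if a subject requires < 20 mg TIW". Section 16.2 (Appendix 2) says the same. Section 11.3.1.1, however, plans a summary of Hb and weekly dose for "subgroups of subjects treated on BIW or QW (including any frequency" below QW) for at least 56 days.

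**The concern.** The step-down is written as an exception to TIW dosing, so those two statements can be read together. The spacing sentence is different. It follows the exception, carries no frequency qualifier, and sets a maximum gap shorter than two of the listed reduced schedules. Read literally, it applies to every roxadustat subject, including those just moved to QW or every 2 weeks.

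Roxadustat is self-administered from instructions given at dispensing, so it matters that the protocol gives one answer on when the next tablet is due. The subjects concerned need very little drug to hold their Hb. After Week 24, scheduled visits are 4 weeks apart (Section 4.1.2), so a misunderstanding could last until the next scheduled Hb check.

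The SAP point is separate and smaller. A reader who takes the design from SAP Sections 3 and 16.2 would conclude that no schedule less frequent than QW exists, although the protocol allows one and the SAP's own Section 11.3.1.1 expects it.

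**Working it through.** **Inputs (Protocol 6.4.1).** Minimum gap 2 days; maximum gap 4 days; trigger below 20 mg TIW; schedules TIW, BIW, QW and every 2 weeks.

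**The section's own figure.** 20 mg × 3 doses = 60 mg per week. This reproduces the stated weekly equivalent.

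**Method.** For each schedule, take every fixed pattern of dosing days that repeats each 7 days (each 14 days for every 2 weeks). List the gaps between consecutive doses and check whether all lie between 2 and 4 days.

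| Schedule | Possible sets of gaps (days) | Sets within 2 to 4 days | Excess over 4 days |
|---|---|---|---|
| TIW | 1-1-5, 1-2-4, 1-3-3, 2-2-3 | 2-2-3 | none |
| BIW | 1-6, 2-5, 3-4 | 3-4 | none |
| QW | 7 | none | 7 − 4 = 3 |
| Every 2 weeks | 14 | none | 14 − 4 = 10 |

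TIW and BIW can each be scheduled within the rule. QW and every 2 weeks cannot be under any choice of days. The open-ended ending of the step-down list would allow longer gaps still, which would also fail.

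**Search for an exception.** The step-down text in the Synopsis, Sections 2.6 and 4.5.3.1 and Appendix 2 was read for any limit on the spacing rule. None is given.

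**Frequencies by document.**

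| Place | Reduced frequencies covered |
|---|---|
| Protocol 6.4.1, Synopsis, 2.6, 4.5.3.1, Appendix 2 | BIW, QW, every 2 weeks and beyond |
| SAP 3 and 16.2 | BIW or QW only |
| SAP 11.3.1.1 | BIW, QW and anything below QW |

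SAP Sections 3 and 16.2 therefore differ from both the protocol and SAP Section 11.3.1.1. The QW option that they do allow also exceeds the 4-day maximum.

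**The case against.** The best reply is that the section can be read sensibly. It opens with TIW, makes a narrow exception, tells subjects to follow their dosing schedule, and then gives general advice on spacing. A site that has just prescribed QW has little reason to think the spacing sentence cancels that prescription. Appendix 2 requires the Medical Monitor to be told of such a change. Both instructions say should rather than must. Section 9.7 does not treat roxadustat dosing that follows clinical circumstances as a deviation, apart from Hb of 13 g/dL or more and overdose.

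Much of this stands. It makes an actual dosing error less likely and limits deviation reporting. It does not remove the conflict: two incompatible recommendations remain incompatible, and the text nowhere limits the spacing to particular frequencies.

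Three stronger readings are tempting, and the documents do not support them.

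- **Excess exposure.** A 4-day maximum implies at least 7/4 = 1.75 doses per week, which is 1.75 times QW and 1.75/0.5 = 3.5 times every 2 weeks. A reader might infer overdosing of that size. The ratios assume that a subject departs from the prescribed schedule at unchanged tablet strength, and nothing shows that this would happen. At the lowest strength, 20 mg, 1.75 doses are 35 mg per week, still below the 60 mg per week trigger.
- **Compliance and the PPS.** If expected doses were counted from the 4-day rule, a fully adherent QW subject would score 1/1.75 = 57% and an every-2-weeks subject 0.5/1.75 = 29%, both under the 75% cut-off in SAP Section 5.2.5. However, dosing compliance in SAP Section 9.2 divides the dose taken by the prescribed dose, and Section 9.1.1 derives weekly dose from the prescribed frequency. The per-dose measure in Section 9.2 refers to expected administrations but does not tie them to the spacing sentence. That sentence enters no SAP formula.
- **A gap in the analysis.** A reader of SAP Section 3 might infer that every-2-weeks subjects have no planned summary. Section 11.3.1.1 includes them.

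**Conclusion.** The conflict is confirmed as written. Protocol Section 6.4.1 gives two instructions that cannot both be followed by subjects on QW (3 days over the stated maximum) or every 2 weeks (10 days over). Subjects on TIW or BIW are unaffected, provided their dosing days are spaced 2-2-3 or 3-4. This rests on reading days apart as the difference between dosing days, and on the spacing sentence applying as written, without an implied restriction to TIW.

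The mismatch in SAP Sections 3 and 16.2 is also confirmed, as a descriptive inconsistency and not a missing analysis.

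The consequences are limited. The documents do not say how many subjects would step down this far. The point changes no sample size, power or margin figure, and the US primary analysis uses the ITT population. No effect on compliance, PPS membership or any other statistical figure has been shown. The reason to act is that the instruction governs a self-administered drug and the correction is nearly free. No view is taken on which interval or frequency is right.

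**What to change.** The texts must be reconciled.

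1. In Protocol Section 6.4.1, state to which dosing frequencies the 2-to-4-day spacing applies, so that the sentence no longer conflicts with the reduced schedules. Whether it covers them, and what spacing they should have, is for the sponsor's clinical team.
2. In SAP Sections 3 and 16.2, bring the list of permitted reduced frequencies into line with the protocol, so that they also agree with Section 11.3.1.1.

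The cost is about one clause in the protocol and a matching edit in two SAP sections. No analysis, sample size or data collection changes.

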## 6.4.2 Epoetin Alfa

During the Treatment Period, starting from Day 1, all subjects on HD randomized to epoetin alfa arm will receive epoetin alfa intravenously TIW irrespective of their baseline route of administration or frequency of ESA use. Epoetin alfa dose adjustments should be based on the country specific package insert or SmPC.

Subjects requiring ultra-low dose of EPO (eg,  $\leq 1000$  IU/per week), frequency of administration may be adjusted per local standard of care. For peritoneal dialysis subjects and home hemodialysis subjects, the route of administration (IV or SC) may remain the same as baseline. However, if the investigator decides to change the route of administration in PD subjects from SC to IV after randomization it should be done during the early part of the treatment phase (preferably prior to Week 16).

In case of a change in route of administration from subcutaneous to intravenous (TIW), the initial dose of IV epoetin alfa will be determined by the investigator per local standard of care.

All epoetin alfa administrations should be performed by the investigator or an authorized member of the site staff or other trained personnel. In PD and HHD subjects, epoetin alfa may also be self-administered subcutaneously by the subject or a caregiver after adequate training or, if in the opinion of the investigator, the subject or a caregiver is already adequately self-administering ESA prior to the study.

## 6.5 Overdose, Emergency Procedures and Management of Overdose

The maximum tolerated dose of roxadustat has not been established in humans. For the purpose of this study, the maximum allowed roxadustat dose is set at 400 mg or 3.0 mg/kg/dose, whichever is lower. Any dosing exceeding the maximum allowed roxadustat dose should be reported within 24 hours. The Medical Monitor should be contacted as soon as possible. Symptoms associated with overdosing, if any, will be reported as adverse events. An overdose without associated symptoms is not an AE and will be recorded on the overdose eCRF only.

In the event of suspected roxadustat overdose, the subject should receive supportive care and monitoring. The Sponsor's Medical Monitor should be contacted as applicable.

In the event of suspected epoetin alfa overdose, refer to the Package Insert or SmPCs.

## 7 ASSESSMENT OF EFFICACY

### 7.1 Study Procedures by Visit

During study visits, unless otherwise indicated, it is preferred that all assessments including labs and physical examinations should be completed predialysis for subjects on HD. For subjects on PD or HHD, assessments may be completed at any time during the visit, but preferably approximately at the same time of the day at each study visit. Quality of life assessments should be administered approximately at the same time of the day. For example, in subjects on HD, these assessments should be completed approximately at the same time during dialysis and in subjects on PD or HHD approximately at the same time of the day. Weight measurement in HD subjects should be done after dialysis (dry weight). For dose adjustment if the post-dialysis weight of the current visit is not available, post-dialysis weight of the prior dialysis session or last recorded post-dialysis weight may be used. Blood pressure and HR should be assessed according to the guidelines described in Appendix 5.

#### 7.1.1 Screening Period

Subjects must be consented before any screening tests or assessments are performed. All screening procedures should be completed within 6 weeks. For subjects currently taking Mircer®, the screening period can be extended up to 8 weeks. During the screening period eligibility assessments will be performed.

Subjects in screening will continue their existing ESA therapy for the treatment of anemia associated with ESRD.

##### 7.1.1.1 Screening 1

- Signed written informed consent
- Inclusion/Exclusion criteria verification
- Demographics and medical history
- Height and weight (use dry weight in HD subjects)
- Vital signs (BP, HR, respiratory rate [RR], and temperature [Temp])
- Laboratory tests:
  - Complete blood count (CBC) with WBC differential
  - Serum chemistry
  - Serum lipid panel
  - Serum iron, ferritin, total iron-binding capacity (TIBC), unsaturated iron-binding capacity (UIBC), transferrin saturation (TSAT)
  - Reticulocyte count and hemoglobin in reticulocytes (CHr)
  - Hemoglobin A1c (HbA1c)
  - Vitamin B12 and folate
  - Enzyme-linked immunosorbent assay (ELISA) for HIV
  - Hepatitis B surface antigen (HBsAg)

- Anti-HCV Ab
- Review and record concomitant medications
- Review and record procedures and nondrug therapies
- Review and record AEs, if any (capture the event under medical history, if applicable)

#### **7.1.1.2 Screening 2 (≥ 2 days apart from Screening 1)**

Hemoglobin values must be obtained at least 2 days apart.

- Vital signs (BP, HR, RR, and Temp)
- Laboratory test:
  - Hemoglobin (Hb) only
  - Serum human chorionic gonadotropin (hCG) pregnancy test for female subjects of childbearing potential only [not required for females of no childbearing potential e.g. postmenopausal (per discretion of the PI), surgically sterile etc.]
- Complete physical examination
- Renal ultrasound - not required if results of a previous renal ultrasound or other imaging within 12 weeks prior to randomization to rule out renal cell carcinoma are available. If no results are available, a renal ultrasound must be performed during the screening period prior to randomization. Renal ultrasound can be done at any time between Screening 2 and randomization, as convenient. The report must be reviewed prior to randomization.
- Review and record concomitant medications
- Review and record procedures and nondrug therapies
- Review and record AEs, if any (capture the event under medical history, if applicable)

#### **7.1.1.3 Additional Screening Assessments**

If a subject's laboratory results do not meet the eligibility criteria, the laboratory assessment may be repeated within the Screening Period. The visits must be at least 2 days apart.

For example, an additional Hb value may be collected if necessary. The mean of the 2 most recent Hb values during the screening period, obtained at least 2 days apart, will be used to calculate the subject's eligibility. Liver function test (LFT) parameters may not be repeated if found exclusionary at Screening without a prior approval from the Medical Monitor unless the investigator has a valid reason to believe that the original lab result is due to an error (eg, possible sample mix-up). Such repeat should be communicated to the Medical Monitor as soon as possible.

A subject who fails screening may be rescreened if deemed appropriate by the investigator. Where possible, an approval should be obtained from the Medical Monitor prior to rescreening.

For all screen failures, the reason(s) will be documented.

#### **7.1.1.4 Randomization**

Eligible subjects will be randomized via IWRS based on stratification factors to receive roxadustat or epoetin alfa. Randomization must take place prior to administration of study drug.

### 7.1.2 Treatment Period

The Treatment Period begins on the first day of dosing with study treatment (Day 1/Week 0) which should correspond to the administration of the subject's next dose of their current ESA treatment. At the Day 1, subjects randomized to Roxadustat Arm will discontinue prior ESA therapy and initiate roxadustat therapy; subjects randomized to Epoetin-Alfa Arm will receive epoetin-alfa irrespective of their prior ESA use. All study procedures must be completed prior to administration of the 1st dose of study treatment.

Subjects on long-acting ESAs (Aranesp or Mircera) may not receive the 1st dose of study medication on the day of randomization due to ESA dosing schedule (e.g. once weekly or once bi-weekly); in these subjects, the 1st dose of study medication (roxadustat or epoetin-alfa) should be administered on the day when the next dose of current ESA would have been due. For all practical purposes, the date of 1st dose of study drug administration should be considered as Day 1.

During the Treatment Period, subjects will attend weekly study visits from Day 1 to Week 2, followed by every two weeks study visits from Weeks 4 to 24. Following Week 24, study visits will occur every four weeks until the EOT. A common closeout will occur when a predetermined number of CV events have been accrued.

#### 7.1.2.1 Day 1 (Week 0)

The following assessments must be completed prior to study drug administration.

- Inclusion/Exclusion criteria verification
- Complete physical examination
- Weight (dry weight in HD subjects)
- Vital signs (BP, HR, RR, and Temp)
- 12 Lead ECG
- Laboratory tests:
  - CBC with WBC differential
  - Serum chemistry
  - Serum lipid panel
  - Serum iron, ferritin, TIBC, UIBC, TSAT
  - Reticulocyte count, CHr
  - HbA1c
  - Special laboratory analytes: High-sensitivity C-reactive protein (hs-CRP) and hepcidin and
  - Archival serum and plasma samples
- Local Hb
- Health Related Quality of Life (HRQoL) Assessments (SF-36, Functional Assessment of Cancer Therapy-Anemia [FACT-An], and EQ-5D-5L).

- Review and record concomitant medications
- Review and record procedures and nondrug therapies

Review and record baseline conditions, AEs, if any (capture the event under medical history, if applicable).

Dispense study drug.

